6.1.8 Dose Adjustments/Modifications/Delays

If no activities in lesions on 0.9mg group, IRC will decide whether to promote higher dose level or not.

6.1.9 Duration of Therapy

Patients will be administered a single dose of SNA002. The duration of study participation will be approximately 42 days, including a screening period up to 14 days and a follow-up period up to 28 days (patients who experience AEs will be followed until resolution).

6.1.10 Tracking of Dose

SNA002 will only be intravenously injected once in the trial.

6.2 Study Agent Accountability Procedures

The complete drug is configured with $^{68}\text{Ge}/^{68}\text{Ga}$ generator at GMP environment in nuclear department or shipped to the site after it was configured at the drug dispensing center generator and received by personnel authorized by the principal investigators.

7 Study Procedures and Schedule

7.1 Study Procedures/Evaluations

- Medical history: including personal history, past history, allergy history, and cancer history
- Medication history: including cancer medication history.

- Physical examination: including height, weight, head, chest, neck, face, abdomen, limbs, skin, lymph, nervous system.
- Radiographic: Pet-ct needed in independent SOP.

7.2 Laboratory Procedures/Evaluations

7.2.1 Clinical Laboratory Evaluations

Blood biochemistry	Blood routine	Electrolyte	Urine routine	Coagulation function	Thyroid function	Serum virology
Total protein	Red blood cell count	Potassium	Bacterial count	Prothrombin time	Thyroid function	Hepatitis B
Albumin	Sodium	Sodium	Glucose	Thrombin time	Triiodothyronine	Hepatitis C
Total bilirubin	Calcium	Calcium	Red blood cells	Fibrinogen	Thyroxine	Syphilis-specific
Alanine aminotransferase	Hemoglobin		White blood cells			HIV antibody
Aspartate aminotransferase	Platelet count					
alkaline phosphatase	Neutrophil count					
Glucose	Lymphocyte count					
Creatinine	Monocyte count					
Blood urea nitrogen						

7.2.2 Other Assays or Procedures

Anti-SNA002 antibody: Blood samples are collected within 30 min before drug administration and on D6±1d, D28±2d during the safety follow-up. All blood samples are tested in the central laboratory.

Radiation exposure of subjects: The radiation exposure is calculated using OLINDA software. Radioactivity uptake of each organ are input into EXM. Double exponential fitting is performed for each organ. Then OLINDA calculates the decomposition of the drug in each source organ and the radiation doses of all target organs. The organs covered in the fitting calculation include but are not confined to brain, chest, bladder, lungs, liver, kidneys, spleen, gastrointestinal tract, and thyroid glands.

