Study Design	
Overall Study Design
 
This is an open-label, dose escalation study to evaluate the safety, PK, biodistribution, dosimetry, and tumor targeting potential of SNA002 in patients with solid tumors.
 
This study will consist of Screening Period, Baseline Period, Study Period and Safety Follow-up Period. A signed and dated informed consent form will be obtained before any study-related procedures are performed. Collect CT/MRI/PET/CT results from subjects within one month before screening to obtain baseline tumor assessment. Eligible patients will be enrolled at least two days before the administration of study drug. The radiation dose for all dose groups at the time of administration should be ranged from 37 to 200MBq. Four dose levels of NOTA-SNA002 are planned: 0.1mg, 0.3mg, 0.5mg and 0.9mg. The final drug product administered to the patient is [⁶⁸Ga]Ga-NOTA-SNA002. Three to seven patients will be sequentially enrolled into each dose cohort. Patients will be administered a single dose of SNA002 over 1 minute as an intravenous bolus. Patients will be observed for 6±1h and 24±6h post infusion for infusion-related and other adverse reactions. In the first cohort of patients, whole body imaging will be acquired using PET/CT at 15±5 minutes, 60±10 minutes and 120±20 minutes post-injection. Before each imaging, the patients need to empty bladder as much as possible. Total-body PET-CT scans can be performed on 1-2 subjects in a certain dose group or each dose group, covering at least one of the aforementioned time points. In the subsequent cohorts,

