	
the imaging schedule may be modified based on the imaging data from the first cohort of patients.
 
The optimal time point for PET scanning will be determined based on the analysis of the tumor to background ratio and tumor to blood pool ratio at different timepoints. Tumor to background ratio is defined as the ratio between tumor tracer uptake and the radioactivity on the opposite site or gluteus maximus, etc. The first PET scan will be performed in combination with a low-dose CT scan for attenuation correction and anatomic reference. An independent radiology review committee (IRC), consisting of principal investigator and nuclear medicine physicians, will be established to evaluate all imaging data.
 
If there is no radioactivity or a small amount of radioactivity in the target lesion as evaluated by the IRC, and the safety criteria are met, the dose will be escalated per the escalation guidelines. If the tumor to background ratio is high per the IRC, three patients will be enrolled at the next higher level and the IRC will determine whether dose escalation should stop based on the imaging data from these three patients. Blood samples will be collected from a peripheral vein to evaluate ADA, PK and the radioactivity in the circulation.
 
 • The time points for blood sample collection are as follows: within 30 minutes before injection of SNA002, at 2 ± 1 minutes, 5 ± 1 minutes, 10 ± 1 minutes, 30 ± 2 minutes, 50 ± 5 minutes, 100 ± 5 minutes and 150 ± 10 minutes post injection. All blood samples are sent to the central laboratory for PK analysis. Radioactivity in the blood sample (whole blood and serum) will be obtained using a γ-well-type detector and measured activity concentrations will be converted to percentage injected activity/L. • Urine sample will be collected to evaluate the renal excretion of radioactivity before injection, at 90 ± 30 minutes, 180 ± 30 minutes and 300 ± 30 minutes post injection. Counts in aliquots of serum or urine will be obtained using a γ-well-type detector and measured activity concentrations will be converted to percentage injected activity/L. 
Blood samples will be taken 30 minutes before administration, on $D6\pm 1$d and $D28\pm 2$d, and will be sent to the central laboratory for ADA analysis. Patients were discharged from the study after blood samples were collected on $D28\pm 2$d. Following the last PET scan, tumor biopsies or operation (if surgery is available) will be obtained. The investigator will determine the number and location of lesions for biopsy for each patient in consultation with the surgeon or interventional radiologist; these should be easily accessible and have positive or negative tracer uptake. Biopsy sites should not exceed 5 for each patient and ideally include both negative lesions and positive lesions. If taken an operation on tumor, the IRC will observe IHC result of tumor and PET scan.
 
The study will be end for patient after completing blood collection on $D28\pm 2$d.
 
Region-of-Interest Definition
 
Regions of interest (ROIs) will be used to determined SNA002 uptake in different organs. Organs with tracer uptake will be drawn using PMOD software based on the PET image, including all activities on the PET images that are contributing to the organ. For organs without tracer uptake, organ delineation will be based on CT data.
 
To calculate the biodistribution and dosimetry in normal organs with tracer uptake, a semiautomatic (region grow) method will be used to delineate the ROI on the PET images. For normal organs without tracer uptake, the ROI will be delineated based on CT scan.
 
Dosimetry
 
Time-activity curves were derived from volumes of interest for each source organ (i.e., brain, heart, lungs, liver, spleen, kidneys, and thyroid) delineated on the whole-body images using PMOD.
 
To define volumes of interest (VOIs) the dynamic study was loaded with all or some frames averaged, depending on the evaluated organ. VOIs were defined manually for heart, liver, gallbladder, kidneys with all frames averaged.
 
Using the PMOD software the VOIs consisted of regions of interest (ROIs) which were defined at the outer contour of the organ. In this way (decay-corrected) TACs of the organs' average radioactivity concentrations and their volumes were obtained.
 
An example, FYI: Source Organs: For dosimetric calculations, the following source organs were included: kidneys, red marrow, cortical bone mineral surface, trabecular bone mineral surface, urinary bladder content, and remainder body. Red marrow activity uptake was estimated from venous blood sampling.
				

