4.2 Study endpoints

Primary Endpoints

- Incidence of treatment-emergent adverse events (TEAEs) and serious adverse events (SAEs)
- Dosimetry and biodistribution

Secondary Endpoints

- Radiation dosimetry of SNA002
- Radiation exposure: detecting radioactivity in the blood
- Recommended diagnostic dose of SNA002
- Optimal imaging window
- SUV_{max} (Standardized uptake value), SUV_{mean}, tumor to background ratio, and tumor to blood ratio.
- PK parameters of SNA002: Including but not limited to maximum serum concentration (C_{max}), time to reach maximum serum concentration (T_{max}), and area under the serum concentration versus time curve from time zero to time (AUC_{0-τ}), and terminal half-life (T_{1/2}).
- Immunogenicity: incidence of anti-drug antibodies

5 Study Enrollment and Withdrawal

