7.3.3 Study Period

D1

- 1) Following successful enrollment at screening, intravenous catheter (for blood sampling) will be placed in regular locations (eg, superficial veins of the upper extremities, superficial veins of the lower extremities, etc.)
- 2) ADA: Collect blood samples within 30 min prior to administration for the detection of anti-SNA002 antibody in the central laboratory.
- 3) Administration drug: another indwelling needle (used for administration) was placed on the contralateral side of the blood collection vein, $[^{68}\text{Ga}]$ Ga-NOTA-SNA002 was slowly injected intravenously, the injection time was not less than 1 min, and extubation was performed after another 10 ~ 20 ml of normal saline was injected, and radiation protection treatment was

performed on the indwelling needle and syringe, and the whole process followed the aseptic operating principles of clinical diagnosis and treatment. Before administration, subject should drink no less than 500 mL of water for hydration.

4) Blood sampling: Blood sampling time points are shown in the table below. ^{68}Ga in the blood samples and centrifugated serum samples are measured using a γ counter within 30 minutes after collection and should be centrifuged within 10 minutes after measuring and the samples are sent to the central laboratory for SNA002 detection.

Blood sampling time (D1)							
Within 30 min before administration	2min ($\pm 1\text{min}$)	5min ($\pm 1\text{min}$)	10min ($\pm 1\text{min}$)	30min ($\pm 2\text{min}$)	50min ($\pm 5\text{min}$)	100min ($\pm 5\text{min}$)	150min ($\pm 10\text{min}$)

5) Systemic PET/CT: Perform whole-body PET-CT scans on subjects after 15 ± 5 minutes, 60 ± 10 minutes, and 120 ± 20 minutes of administration. Panoramic PET-CT scans performed after dosing were acceptable for 1 to 2 subjects in a dose group or each dose group and were required to cover at least one of these time points.

6) Urine sampling: Urine samples are collected at 90 ± 30 min, 180 ± 30 min, and 300 ± 30 min after administration, and ^{68}Ga in urine samples are measured using a γ counter.

7) Measurement of radiation dose: Surrounding radiation dose is measured at 4 ± 0.5 h after administration.

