9. ADA: blood samples were collected within 30 minutes before administration, on D6 ± 1d and D28 ± 2d during the safe follow-up period. All blood samples were tested in an independent third-party central laboratory.
10. Systemic PET-CT: Three systemic PET CT scans are performed at 15±5 minutes, 60±10 minutes, and 120±20 minutes after administration. Panoramic PET-CT scans performed after dosing were acceptable for 1 to 2 subjects in a dose group or each dose group and were required to cover at least one of these time points.
11. Measurement of Radiation Dose: measure the surrounding radiation dose at 4 ± 0.5 hours after administration.
12. PD-L1 Immunohistochemical Examination and Formulate a Plan for Obtaining Target Lesion Specimens (If Performed) : Obtain the PD-L1 immunohistochemical results of the subjects at the study site during the screening period. This experiment determines whether to collect tissue specimens after administration based

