10.4.4 Safety Analyses

Safety evaluation indicators

- AE/SAE/SUSARs.
- Vital signs: Blood pressure, pulse, respiration, and body temperature.
- Physical Examination: Assessment of changes in physical examination of subjects before and after drug administration.
- Laboratory tests: Blood routine, blood biochemistry, urine routine, and coagulation function.
- Electrocardiogram: Evaluate changes in subjects' electrocardiogram before and after administration.
- Examination of injection site: Evaluate the condition of the injection site after administration, such as redness, swelling, heat, pain, itching, etc.
- Systemic and organ radiation distribution: Regions of interest (ROI) such as the brain, liver, and heart are delineated based on the iteratively reconstructed PET/CT imaging results to obtain the mean and maximum tumor volume radioactivity at different time points. The radioactive decay of each source organ and the radiation dose of all target organs are calculated.
- Radiation exposure in ambient environment: Radiation exposure in ambient environment measured by a radiation detector.
- Researcher exposure: such as recording exposure through personal radiation dosimeters worn by researchers.

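### Section 7.2.2 asks for a double-exponential fit per organ from three PET scans, which cannot determine it, and applies the same rule to the bladder, which is emptied before each scan

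*Combined protocol and SAP*

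**What the plan says.** Section 7.2.2 has organ uptake fitted and passed to OLINDA: "Double exponential fitting is performed for each organ". Its organ list includes bladder. It states no fixed parameter, fallback model or rule for activity after the last scan.

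The imaging data are set by note 10 to Table 4 (section 7.3.7): "Three systemic PET CT scans are performed at 15±5 minutes, 60±10 minutes, and 120±20 minutes after administration". Panoramic scans in one or two subjects "were required to cover at least one of these time points" (section 7.3.3). The Protocol Summary adds that in later cohorts "the imaging schedule may be modified based on the imaging data from the first cohort of patients". Its Dosimetry text also says "the dynamic study was loaded with all or some frames averaged, depending on the evaluated organ", but no dynamic acquisition appears in section 7.3.3 or Table 4.

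On the bladder, the Protocol Summary says "Before each imaging, the patients need to empty bladder as much as possible". Section 10.4.4 derives organ dose from regions "delineated based on the iteratively reconstructed PET/CT imaging results", with brain, liver and heart as examples. Urine is collected at 90±30, 180±30 and 300±30 min, counted, and expressed as percentage of injected activity per litre. Its stated uses are renal excretion (Protocol Summary), renal clearance from pooled urine (Table 4, note 8) and change in sample radioactivity (section 10.4.2).

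Section 4.2 lists "Dosimetry and biodistribution" as a primary endpoint.

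**The concern.** Two analysts following section 7.2.2 exactly could fit different curves through the same three points and report different organ doses. Nothing in the text guarantees a fourth time point: the panoramic scans may repeat an existing time, and the possible schedule change names no added time. Nor does 7.2.2 say whether physical decay is put back into the decay-corrected curves that the Protocol Summary describes.

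The bladder raises a different problem. A bladder that fills and is emptied repeatedly does not follow a smooth two-exponential curve, and images taken after voiding show only the residual. Urine could supply the rest, but a concentration per litre cannot be turned into excreted activity without a volume. Section 6.1.6 has subjects drink before dosing and drink and void repeatedly afterwards, so the concentration also depends on dilution. Section 6.1.7.1 names kidneys and bladder as the excretion organs. A fitting rule can still be written later in the SAP; a volume that was never recorded cannot be recovered.

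**Working it through.** **Inputs from the document.** Double exponential per organ (7.2.2); scans at 15±5, 60±10 and 120±20 min (Table 4, note 10); half-life of 68 min (6.1.2); urine times and unit (Protocol Summary). The document gives no organ kinetics, so every curve below is assumed and noise-free.

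**1. Parameter count.** A(t) = A1·exp(−λ1·t) + A2·exp(−λ2·t) has 4 parameters. Residual degrees of freedom are 3 − 4 = −1. The Jacobian at 15, 60 and 120 min has rank 3 of 4 in all five assumed shapes. With one constraint (zero activity at injection, or one rate fixed at physical decay) there are 3 parameters and 3 points: the fit is determined, with 0 degrees of freedom to check it.

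**2. Share resting on extrapolation.** Under physical decay alone, the fraction of time-integrated activity after the last scan at time T is exp(−ln2·T/68): 0.29 at 120 min, 0.36 at 100 min and 0.24 at 140 min.

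**3. Spread over exact fits.** Time-integrated activity is A1/λ1 + A2/λ2. The shapes (biological half-lives, each multiplied by 68-min decay) were:
- washout 10/240 min (weights 0.6/0.4) and 20/300 min (0.5/0.5);
- uptake 10 min with retention, uptake/clearance 5/240 min and 20/600 min.

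Fits were kept if they passed exactly through the three points, stayed non-negative, had both rates at or above ln2/68, and had a fast effective half-life of 5 to 60 min.

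| Case | Ratio to true time-integrated activity |
|---|---|
| Uptake shapes, nominal times | 0.925–1.033 |
| Washout shapes, nominal times | 0.99–1.07 |
| All five shapes, eight corners of the scan windows | 0.86–1.16 |
| Further shape: uptake 20, clearance 120 min | 0.975–1.00 |
| Further shape: washout 10/120 min (0.8/0.2) | 0.99–1.16 |

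The 5-min floor matters. Admitting a fast phase of 4 or 3 min raises the upper limit for washout shapes at nominal times to 1.16 or 1.42. No passage suggests so fast a phase.

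**4. What one constraint does.** For a 20/300 min washout with amplitudes 6 and 4, the true value is 453.7. Fixing the slow rate at physical decay gives 464.9, and 464.9/453.7 = 1.02. Zero activity at injection recovers the uptake shapes exactly in the absence of noise.

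**5. Bladder from images alone.** Assumed: first-order excretion with half-time 30, 60 or 120 min; voids at 10, 55, 115, 180 and 300 min; post-void residual 5, 10, 20 or 30%. The post-void activity at 15, 60 and 120 min was integrated by trapezoid with a physical-decay tail, the first 15 min being taken either as a linear rise from zero or as constant. The result was 0.28–0.67 of true bladder time-integrated activity.

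**6. Early voids.** The first post-dose urine window opens at 90 − 30 = 60 min. Voids before the 15- and 60-min scans can fall earlier. If those at 10 and 55 min are not kept, the later collections hold 31–73% of the activity voided by 300 min in the same model.

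**7. Unit.** The same 10% of injected activity reads 10/0.2 = 50 %/L in 0.2 L and 10/0.8 = 12.5 %/L in 0.8 L.

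**The case against.** The strongest reply on the organs is that little hangs on the non-uniqueness and that a stated constraint is enough. That stands. A reader might infer from the parameter count that organ doses would be badly wrong, or that exponentials should be banned in favour of a trapezoid. The figures support neither. A linear-rise trapezoid with a physical-decay tail gave 1.07 for uptake 20/clearance 120 min, where exact fits gave 0.975–1.00, and 0.89 for the 10/120 min washout, where they gave 0.99–1.16. It exchanges an ambiguity for a fixed bias.

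On the bladder, a reader might infer that urine volume goes unrecorded and that bladder activity will be understated by a third or more. The document does not establish this. Pooling for clearance (Table 4, note 8) and the counting of aliquots may imply a known volume. Specimen handling is deferred to a laboratory manual (7.2.3) and PET-CT to an SOP (7.1), neither of which is available here. The regions in section 10.4.4 are examples that do not name bladder. Urinary bladder content does appear as a source organ in the Protocol Summary, though only in a list marked as an example. What remains is that no passage connects urine to the bladder model or asks for volume, while 7.2.2 puts bladder under a rule unsuited to it.

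Endpoint status is also mixed: radiation dosimetry is repeated as a secondary endpoint in 4.2 and is a secondary objective in section 3.

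**Conclusion.** The concern holds in two parts of unequal weight.

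- **Bladder and urine: should be fixed.** The exponential rule does not suit an organ emptied before each scan, and the information needed for a better rule must be captured prospectively. The 0.28–0.67 range is conditional on images alone being used and on assumed excretion, void times and residuals. No effect on bladder-wall or effective dose was calculated.
- **Other organs: minor.** The fit is not unique as written. The effect on time-integrated activity in assumed curves is about 0.93–1.07 at nominal times, and reaches 0.86–1.16 at the window edges, given a fast effective half-life of at least 5 min.

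Confidence is high only for the parameter count. Image-only bladder dosimetry and unrecorded volume are plausible readings, not shown facts.

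**What to change.** 1. **Section 7.2.2, organs.** Replace the unconstrained double exponential with one pre-specified method that three scans can determine. Options are zero activity at injection for organs showing uptake, one rate fixed at physical decay, or a trapezoid with a physical-decay tail. Use non-decay-corrected activity at actual scan times, and name one alternative as a sensitivity analysis. Exponentials need not be excluded.
2. **Bladder and urine.** Take bladder out of the exponential fit. Keep all urine from injection to the 300-min collection, including pre-scan voids, and record time, volume and activity of each void. Report cumulative percentage of injected activity excreted. Derive bladder content from voided activity plus the post-void image residual, stating the starting value after each void and the rule after 300 min. If the laboratory manual already requires volumes, cite it in the protocol.
3. **Protocol Summary.** Reconcile the reference to a dynamic study with the three-scan schedule.

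The cost is wording plus a small recording burden on urine that is largely collected already. No organ method can be checked for fit with three points, and a physical-decay tail slightly overstates activity where biological clearance continues. In the assumed voiding model, a bladder rule of this kind, with decay-corrected content interpolated linearly between voids, overstated activity by about 5–15%.

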7.2.3 Specimen Preparation, Handling, and Storage

See details in central laboratory manual.

